8.2.5 Serious Adverse Event Reporting to the Coordinating Center

All Adverse Events will be reported to regulatory authorities, IRB/IECs and investigators in accordance with all applicable global laws and regulations.

All serious adverse events and all Events of Clinical Interest that have been specified to require expedited reporting occurring on this study require expedited reporting to the University of Chicago Comprehensive Cancer Center (UC CCC). The responsible Research Nurse or other designated individual at the treating site should report the SAE to the Principal Investigator and the Cancer Clinical Trials Office (CCTO) by the end of the business day when s/he becomes aware of the event. Events occurring after business hours should be reported to the CCTO by 12pm (noon) the next business day. Reports should be made using the 'Serious Event Report' Form. Please scan and send via email (preferred) or fax to the following:

University of Chicago Phase II CRA General:

[contact]

[contact] [contact]

UC CCC Cancer Clinical Trials Office Quality Assurance:

[contact]

All unexpected adverse reactions must be reported to the IND holder so that the University of Chicago CCTO can inform the FDA. The responsible Research Nurse or other designated individual at the treating site should provide a complete written report using the FDA MedWatch 3500A form. The completed form should be sent to the CCTO at [contact] and to the Phase II CRA at [contact] within the specified timelines below regardless of whether all information regarding the event is available. If applicable, a follow-up report should be provided to the CCTO if additional information on the event becomes available.

Participating sites should not forward any adverse event reports directly to the FDA. The CCTO will report all events to the FDA as per the current FDA guidelines.

Fatal or Life-threatening Events: within 4 calendar days from treating investigator knowledge of the event

All Other Reportable Events: within 10 calendar days of treating investigator knowledge of the event

All serious adverse events should also be reported to the local IRB of record according to their policies and procedures.

8.2.6 Serious Adverse Event Reporting by the Coordinating Center

The designated UC CCC Regulatory Manager will notify all participating sites of all unexpected and serious adverse reactions that occur on this clinical trial and which are reported to the FDA and/or UC Institutional Review Board (IRB). When reported to the FDA, a copy of the completed Form 3500A (MedWatch) will be provided to the responsible Regulatory Manager by the CCTO IND Coordinator for distribution to all participating sites.

8.2.7 Serious Adverse Event Reporting to Merck

Any serious adverse event reported to the UC CCC, whether or not related to Merck product, must also be reported within 2 working days to Merck Global Safety by the responsible Research Nurse or other designated individual at the treating site.

Non-serious Events of Clinical Interest will be forwarded to Merck Global Safety and will be handled in the same manner as SAEs.

SAE reports and any other relevant safety information are to be forwarded to the Merck Global Safety [contact].

9.0 DATA REPORTING

Data reporting will be performed utilizing the eVelos electronic data capture system. The University of Chicago CRA will provide you with the applicable user registration information.

All required data must be recorded in the eVelos database at the completion of each cycle. AEs are to be entered in real time. SAEs are to be entered on the Serious Event Form within 24 hours of the site's knowledge of the event and sent via email (preferred) or fax to the ([contact] University of Chicago [contact]; [contact]). All case report forms must be completed by designated study personnel. Each screened (consented) patient is to be entered into eVelos within 48 hours of patient registration. In addition to direct data entry, you may be required to provide supporting source documentation. Source records are original documents, data, and records (e.g., medical records, raw data collection forms, pharmacy dispensing records, recorded data from automated instruments, laboratory data) that are relevant to the clinical trial. Each site will prepare and maintain adequate and accurate source documents. These documents are designed to record all observations and other pertinent data for each subject enrolled in this clinical trial. Source records must be adequate to reconstruct all data transcribed onto the case report form.

10.0STATISTICAL ANALYSIS PLAN

10.1 Statistical Analysis Plan

The primary endpoint of the study will be response rate by irRECIST criteria. A Simon (Cont Clin Trials, 1980), optimal two-stage design will be employed to test the null hypothesis of a 10% response rate (based on historical ipilimumab alone) vs. a 30% alternative. Twelve

patients will be entered into the first stage and if 1 or fewer responses are observed then the trial will be terminated for lack of activity. Otherwise an additional 23 patients will be enrolled for a total of 35. If 5 or fewer responses are observed the treatment will be considered insufficiently active whereas if 6 or more (>17%) are seen the null hypothesis will be rejected and the treatment considered worthy of further testing. This design has an alpha level of 0.10 (1-sided), 90% power, and a 0.65 probability of stopping early if the true response rate is only 10%. With the closing of cohort 2, we will enroll an additional 35 patients who had initial progression if 6 or more patients respond among the initial 35. This will bring the total sample size to n=70, and provide additional precision for the estimated response rate and other secondary endpoints. For response rate, assuming a true rate of 30%, n=70 subjects will provide a 90% confidence interval width of $\pm 9.0\%$.

Evaluable patients will be defined as any eligible patient who receives a dose of pembrolizumab in combination with ipilimumab.

Secondary endpoints will include estimation of progression-free survival using the Kaplan-Meier method and assessment of changes in biomarkers from pre-post treatment using paired t-tests or Wilcoxon signed-rank tests.

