4.2.3.1 Efficacy Endpoints

The primary efficacy objective of this trial is to evaluate the anti-tumor activity of the combination of pembrolizumab and ipilimumab in subjects with advanced melanoma who

have previously been treated with an anti-PD1/L1 antibody. Response rates per irRECIST will be evaluated.

irRECIST as assessed by the investigator will be used as the primary response rate efficacy endpoint. irRECIST will also be used by the local site to determine eligibility and make treatment decisions. The primary efficacy endpoint is response rate based on irRECIST. Secondary endpoints are listed in section 3.2.

Immunotherapeutic agents such as pembrolizumab may produce antitumor effects by potentiating endogenous cancer-specific immune responses which may be functionally anergic. The response patterns seen with such an approach may extend beyond the typical time course of responses seen with cytotoxic agents, and can manifest a clinical response after an initial increase in tumor burden or even the appearance of new lesions. Standard RECIST criteria may not provide a complete response assessment of immunotherapeutic agents such as pembrolizumab therefore the irRECIST have been developed to encompass this.

Broadly, irRECIST includes the concept of treatment beyond progression, if radiologic imaging shows PD, tumor assessment should be repeated ≥ 4 weeks later in order to confirm PD with the option of continuing treatment per below while awaiting radiologic confirmation of progression. If repeat imaging shows a reduction in the tumor burden compared to the initial scan demonstrating PD, treatment may be continued as per treatment calendar. If repeat imaging confirms progressive disease, subjects will be discontinued from trial therapy. In determining whether or not the tumor burden has increased or decreased, Investigators should consider all target lesions as well as non-target lesions.

In subjects who have initial evidence of radiological PD, it is at the discretion of the treating physician whether to continue a subject on study treatment until repeat imaging is obtained a minimum of 4 weeks later. This decision should be based on the clinical judgment of the subject's overall clinical condition, including performance status, clinical symptoms, and laboratory data. Subjects may receive treatment while waiting for confirmation of PD if they are clinically stable as defined by the following criteria:

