10.2 Sample Size and Expected Accrual

The total sample size will be 70 patients Patient accrual is projected to be approximately 3 patients per month. Thus accrual is likely to proceed for 8 to 24 months.

11.0LABELING, PACKAGING, STORAGE AND RETURN OF CLINICAL SUPPLIES

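### Does the two-stage design in Section 10.1 need a written rule for when the response counts at 12 and 35 patients are read?

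*Combined protocol and SAP*

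**What the plan says.** Section 10.1 makes the irRECIST response rate the primary endpoint. It describes a Simon optimal two-stage design with a 10% null and a 30% alternative. The first decision comes at 12 patients: "if 1 or fewer responses are observed then the trial will be terminated for lack of activity". With 2 or more responses the study goes on to its second stage: "Otherwise an additional 23 patients will be enrolled for a total of 35". Six or more responses among the 35 reject the null, and the same count opens the expansion: "we will enroll an additional 35 patients who had initial progression if 6 or more patients respond among the initial 35". The claimed properties follow: "This design has an alpha level of 0.10 (1-sided), 90% power, and a 0.65 probability of stopping early", the last figure being for a true rate of 10%.

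The definition of a response is in Appendix 13.3, to which the primary objective in Section 3.1 points. A complete or partial response counts as best response only when confirmed on consecutive scans at least 4 weeks apart. Section 4.2.3.1 adds that "irRECIST as assessed by the investigator will be used as the primary response rate efficacy endpoint".

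On timing, the flow chart in Section 6.1 puts on-treatment imaging in cycles 4 and 8. With 3-week cycles these fall at about weeks 9–12 and 21–24. Section 10.2 projects about 3 patients per month and concludes: "Thus accrual is likely to proceed for 8 to 24 months".

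**The concern.** Section 10.1 acts on responses observed, but no section fixes the date or scan at which the observation closes. Evaluability requires only one combination dose, with no minimum follow-up. The early-termination list in Section 5.9 and the monitoring agenda in Section 12.4 do not mention a response look.

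The trial's own schedule makes this more than a formality. Section 4.2.3.1 warns that "The response patterns seen with such an approach may extend beyond the typical time course of responses seen with cytotoxic agents". Its repeat-scan instruction covers progression only ("if radiologic imaging shows PD, tumor assessment should be repeated"), so on the routine schedule a response first seen in cycle 4 is confirmed in cycle 8. At 3 patients per month, few of the first 12 have been scanned when the twelfth enters. Section 10.2 shows no allowance for waiting: 70 patients at 3 per month already take 23.3 of its 24 months.

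Two things would be at stake. A count at 12 taken too early would stop an active regimen more often than the stated 90% power implies. A count that included unconfirmed responses would let an inactive regimen through more often. The trial is open-label and response is investigator-assessed, so an unwritten rule could be settled with the responses in view.

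**Working it through.** **Inputs from Section 10.1.** n1 = 12, stop if at most 1 response; n = 35, reject if at least 6; p0 = 0.10, p1 = 0.30. From Section 10.2: 3 patients per month.

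**1. The plan's own figures.** Let X1 ~ Bin(12, p) and X2 ~ Bin(23, p).

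- Early stop = P(X1 ≤ 1) = (1−p)^12 + 12p(1−p)^11.
- Rejection = Σ over x ≥ 2 of P(X1 = x) · P(X2 ≥ 6−x).

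| True rate | Early stop | Rejection |
|---|---|---|
| 0.10 | 0.2824 + 0.3766 = 0.659 | 0.0977 (alpha) |
| 0.30 | 0.0138 + 0.0712 = 0.085 | 0.9014 (power) |

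These match the stated 0.10, 90% and 0.65. A grid search confirms that stopping at 1 or fewer of 12 and rejecting at 6 or more of 35 is the optimal design for these limits. The calculation gives each of the 12, and each of the 35, a known outcome. The stated figures therefore already presuppose complete assessment at each look.

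**2. Reading the count at 12 too early.** Assume, since the documents give no value, that a share f of eventual responders is countable at that look, that everyone else is scored a failure there, and that the count at 35 is complete. Then the number seen is Bin(X1, f), and enrolment continues if at least 2 are seen.

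| f | Stop at 12, true 30% | Power | Alpha, true 10% |
|---|---|---|---|
| 1.0 | 0.085 | 0.901 | 0.098 |
| 0.9 | 0.125 | 0.864 | 0.088 |
| 0.8 | 0.178 | 0.812 | 0.078 |
| 0.7 | 0.248 | 0.744 | 0.066 |

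An early read costs power and lowers the false-positive risk.

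**3. Counting unconfirmed responses.** Assume a share c of first responses is later confirmed (also not in the documents), with a true confirmed rate of 10%. The unconfirmed rate is 0.10/c.

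| c | Early stop | Alpha, unconfirmed counted at 12 only | Alpha, unconfirmed counted at 12 and 35 |
|---|---|---|---|
| 0.9 | 0.608 | 0.101 | 0.141 |
| 0.8 | 0.547 | 0.105 | 0.204 |

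With confirmed responses at 35, alpha cannot exceed P(X ≥ 6 | 35, 0.10) = 0.132 even with no look at 12 at all. The last column needs unconfirmed responses in the final count, which Appendix 13.3 excludes.

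**4. Calendar.** Patient k has been followed (12−k)/3 months when patient 12 enters. Week 9 is 2.07 months, week 13 is 2.99 and week 21 is 4.83. So 5 of the 12 have reached week 9, 3 have reached week 13, and none has reached week 21. A count on that day would plainly be incomplete.

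Uninterrupted accrual takes 70/3 = 23.3 months. If enrolment waited in full at both looks, the total would be:

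- settled by week 24 (5.52 months each): 23.3 + 2 × 5.52 = 34.4 months;
- first response in cycle 8, confirmed at week 28 (6.44 months): 23.3 + 12.9 = 36.2 months;
- the same, confirmed at week 36 if the four-cycle scan spacing continues (8.28 months): 23.3 + 16.6 = 39.9 months.

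The 8 months in Section 10.2 correspond to 8 × 3 = 24 patients, which is none of the design's sizes (12, 35, 70). They could be 12/3 = 4 months of accrual plus about 4 months of assessment, but the section does not say so.

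**The case for a change.** The strongest case for a change is that the gap is real and a few sentences would close it. No section states a data cut, how a first response awaiting confirmation is treated on the day of a look, or whether enrolment is held. The protocol itself expects late responses, and the first look can end the trial. In an open-label study, a rule fixed in advance is better than one left to judgement.

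The absence of a written data cut stands. Three other parts of the case do not.

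- Confirmation is not open. Section 10.1 adopts irRECIST and Appendix 13.3 states the requirement twice, so the alpha values of 0.141 and 0.204 describe a departure from the plan.
- The power loss needs patients without a settled outcome to be scored as failures. Section 10.1 does not say this, and its order (enter 12, count, otherwise enrol 23) points to assessing each stage first. Central slot registration in Section 7.1 gives the means to wait.
- A confirmatory scan before cycle 8 is not barred. Section 8.1 allows unscheduled procedures when clinically necessary, and Section 5.5.2 refers to a tumor assessment at week 12 as an established point.

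A written rule would also not be free. Requiring every pending response to be resolved before a stop, with enrolment held meanwhile, could take accrual from about 23 months to 36–40. How long to wait is a reasonable matter for the investigators.

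**Conclusion.** This is missing operational detail that analysts would fill sensibly, not an error in the design. The alpha, power and early-stop probability are correct on the reading that their own calculation requires: confirmed responses, with the status of every patient in the stage known. On that reading the false-stop risk at a true 30% is 8.5% and power is 90.1%.

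The fall to 0.86, 0.81 or 0.74 rests on assumed shares of 0.9, 0.8 and 0.7, for which the documents give no support, and on counting unassessed patients as failures. If unconfirmed responses were let in at the first look only, alpha would be 0.101 to 0.105 for c of 0.9 to 0.8, a negligible difference from 0.10.

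The 8-to-24-month range in Section 10.2 is worded as a projection. Its upper end leaves no time for waiting and its lower end is unexplained, but neither enters an estimate, a threshold or a conclusion. The judgement would differ only if the plan directed that the count at 12 be taken before those patients' responses could be known. It does not.

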2.0 TRIAL DESIGN

2.1 Trial Design

Phase II study evaluating the benefit of the combination of anti-PD1 (pembrolizumab) and anti-CTLA4 (ipilimumab) antibodies in advanced melanoma. The study will determine the response rate of the combination and evaluate other clinical parameters such as progression-free survival and safety of the combination following anti-PD1/L1 antibody. The study will also provide the opportunity to investigate blood or tumor based factors that may predict response to anti-PD1 antibody in combination with anti-CTLA4.

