2.2 Trial Diagram

3.0 OBJECTIVE(S) & HYPOTHESIS(ES)

3.1 Primary Objective(s) & Hypothesis(es)

(1) **Objective:** To determine the irRECIST* response rate of pembrolizumab with ipilimumab following initial progression to anti-PD1/L1 antibody (or combination not containing anti-CTLA4) in subjects with advanced melanoma.

*For review of irRECIST see Appendix – Section 13.3

Hypothesis: The combination of pembrolizumab and ipilimumab will induce tumor responses in patients who have been previously treated with anti-PD1/L1 antibody

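### Should the plan carry a second decision rule at 70 patients, given that its conclusion is already fixed at 6 of 35?

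*Combined protocol and SAP*

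**What the plan says.** The primary endpoint is the irRECIST response rate (Section 10.1), tested against a 10% null with a 30% alternative. Twelve patients are entered first, and the trial stops if 1 or none responds. Otherwise 23 more are entered, for a total of 35. With 5 or fewer responses the treatment is judged insufficiently active; "if 6 or more (>17%) are seen the null hypothesis will be rejected and the treatment considered worthy of further testing". The stated properties are one-sided alpha 0.10, power 90%, and a 0.65 probability of early stopping at a true 10%.

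The extension follows in the same paragraph: "we will enroll an additional 35 patients who had initial progression if 6 or more patients respond among the initial 35". Its purpose comes next: "This will bring the total sample size to n=70, and provide additional precision for the estimated response rate and other secondary endpoints". The paragraph then gives a 90% confidence interval of ±9.0 points at n=70 for a true rate of 30%. Section 10.2 gives the overall size: "The total sample size will be 70 patients". Section 2.1 states the general aim: "The study will determine the response rate of the combination".

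**The concern.** The trial is sized at 70, yet its only stated conclusion on the primary endpoint is settled by the first 35. Nothing in Section 10.1 says that the conclusion is looked at again at 70. If 6/35 were followed by 0/35, the report would show 6/70 = 8.6%, with an exact 90% interval of 3.8% to 16.2%, beside a rejected 10% null.

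The general pattern does not need so extreme a case. A treatment that passes by luck at 35 should regress in the next 35, and the plan has no rule for reading that. The pooled rate also exists only when the first 35 did well, so it is biased upward, and the plan does not promise to show the second 35 separately. At stake would be a treatment carried forward on a result that the full data set does not support, when the patients who could have shown this were enrolled anyway.

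**Working it through.** **Inputs.** All come from Section 10.1: stop at 1/12 or fewer; reject at 6/35 or more; null 10%; alternative 30%; extension of 35 patients. The cut-off of 11/70 and the true rates of 15%, 20% and 25% are not in the documents. They are used here only to price the alternative rule. All 70 patients are assumed evaluable, with one common response rate.

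**1. The plan's own figures.** Let X1 ~ Bin(12, p) and X2 ~ Bin(23, p).

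- Early stopping at 10%: P(X1 ≤ 1) = 0.9^12 + 12 × 0.1 × 0.9^11 = 0.2824 + 0.3766 = 0.659 (stated 0.65).
- P(reject) = Σ over x1 = 2 to 12 of P(X1 = x1) × P(X2 ≥ 6 − x1). This gives 0.0977 at p = 0.10 and 0.9014 at p = 0.30 (stated 0.10 and 90%).
- A search over two-stage designs with alpha ≤ 0.10 and power ≥ 0.90 returns 1/12 and 5/35 as the optimal one, with expected size 19.8 under the null.
- Interval at n=70: 1.645 × √(0.3 × 0.7 / 70) = 0.090 (stated ±9.0 points).

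The test is therefore correctly specified at 35. The extension contains no second opportunity to reject, so alpha stays at 0.098.

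**2. How often does 6/70 occur?** It needs exactly 6/35 through the first gate, then no responses in 35. At a true 10% this is 0.0527 × 0.9^35 = 0.0527 × 0.0250 = 0.0013. That is 0.13% of trials, or 0.0013 / 0.0977 = 1.3% of false rejections. At 15% it is 0.04%, and at 20% it is 0.004%.

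**3. What would a rule at 70 buy, and at what price?** With Y ~ Bin(35, p), compare the rule as written with P(X1 ≥ 2, X1 + X2 ≥ 6, X1 + X2 + Y ≥ 11). Eleven is the smallest count that rejects 10% in a fixed sample of 70 at one-sided 0.10 (tail 0.087; 10/70 gives 0.159).

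| True rate | As written | Adding ≥11/70 | Loss (points) | Share of positives reversed |
|---|---|---|---|---|
| 10% | 9.8% | 4.0% | 5.7 | 58.6% |
| 15% | 33.7% | 26.7% | 7.0 | 20.7% |
| 20% | 60.4% | 57.7% | 2.7 | 4.4% |
| 25% | 79.5% | 79.0% | 0.5 | 0.6% |
| 30% | 90.1% | 90.1% | 0.04 | 0.05% |

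The first row is a gain and the others are costs. Requiring 12/70 moves further the same way: 2.4% at a true 10%, with losses of 11.8 points at 15% and 5.9 at 20%.

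**4. Delay.** Section 10.2 projects about 3 patients per month. Holding the conclusion until 70 adds 35 / 3 = 11.7 months of accrual, plus the follow-up needed to read and confirm responses.

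**5. Bias of the pooled rate.** Given expansion, the first 35 average 19.2% at a true 10%, and the second 35 average 10% because they are not selected. The pooled mean is (19.2 + 10) / 2 = 14.6%, a bias of 4.6 points. The bias is 3.0 points at 15%, 1.8 at 20% and 0.5 at 30%. Coverage of the ordinary exact 90% interval, given expansion, is 92% to 95% at true rates of 15% to 30%. It falls to 75% at exactly 10%, where only 9.8% of trials expand.

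**The case for a change.** The strongest argument is the 58.6%. If the true rate is 10% and the trial passes at 35, more often than not it ends at 10/70 or fewer, a count that a fixed test of 70 patients would not call significant at one-sided 0.10. The extension patients are enrolled in any case, and at the 30% design alternative the extra requirement costs almost nothing.

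The arithmetic is right, but it does not show a fault. The 58.6% is a share of the 9.8% of null trials that the sponsor has already accepted as false positives under a limit of 0.10. Any added requirement removes some of them, because it makes the test stricter. The fixed-sample test at 70 used as the yardstick is not one the protocol sets. The conclusion at issue is only that the treatment merits further testing, a screening decision for which a liberal alpha is a reasonable choice. Nothing in the documents says that a true rate of 15% or 20% is of no interest.

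Nor does the extra rule remove the mismatch it is meant to cure. At 11/70 the null would be rejected beside a two-sided 90% interval of 9.1% to 24.7%, which still contains 10%. Moving to 12/70 (10.2% to 26.3%) cures that at a higher cost. That 11, 12 and no rule at all are each defensible shows that none of them is required.

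Two narrower points stand as observations. Section 10.1 does not say that n=70 carries no decision, but the purpose it gives, "This will bring the total sample size to n=70, and provide additional precision for the estimated response rate and other secondary endpoints", already says what those patients are for. It also does not promise a separate estimate from the second 35. That estimate would be free of selection but less precise: 1.645 × √(0.3 × 0.7 / 35) = 12.7 points either side at a true 30%, against 9.0 for the pooled rate. With a pooled bias of 0.5 points at 30% and near-nominal coverage from 15% upward, little depends on it.

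**Conclusion.** The concern does not hold. Section 10.1 gives each half of the trial a distinct role: a Simon test on 35 patients that meets its stated properties (alpha 0.098 against 0.10, power 0.901 against 0.90), then 35 more patients for estimation, with the ±9.0-point precision reproduced. The extension cannot inflate the error rate, and a low pooled rate would be visible in the estimate it supports. The 6/70 example arises in 0.13% of trials at a true 10%.

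A rule of at least 11/70 would be a different design: false positives of 4.0% instead of 9.8%, paid for with 7.0 points at a true 15%, 2.7 at 20%, and about a year's wait. Which to prefer depends on how much a rate of 15% to 20% matters to the sponsor, and the documents do not say. These figures assume 70 evaluable patients with one response rate in both halves. The check of the test at 35 does not depend on the extension at all.

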4.2.3 Rationale for Endpoints

Here we propose a clinical trial testing the hypothesis that the addition of anti-CTLA4 antibody (ipilimumab) to pembrolizumab will generate clinical responses in patients who have had initial progressive disease, or only disease stabilization, to anti-PD1/L1 antibody alone. Preclinical and prior clinical data support this hypothesis and from a practical standpoint, deferral of the toxicities associated with anti-CTLA4 in those patients who do not require exposure to anti-CTLA4 is particularly attractive.

We propose to continue pembrolizumab beyond progression on an anti-PD1/L1 antibody as we believe that single agent ipilimumab will overcome the non-inflamed tumor microenvironment in only a small percentage of patients while the combination of ipilimumab and pembrolizumab may induce responses in as many as 40% of patients based on prior studies. The results of this study may suggest that continuous PD-1 blockade is required to optimize therapy for advanced melanoma and, through our correlative analysis, we hope to propose a model by which we can suggest which patients would benefit from upfront pembrolizumab alone or pembrolizumab in combination with anti-CTLA4 antibody.

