5.1.2 Subject Inclusion Criteria

In order to be eligible for participation in this trial, the subject must:

- 1. Be willing and able to provide written informed consent for the trial.
- 2. Be \geq 18 years of age on day of signing informed consent.
- 3. Have experienced disease progression during treatment with an anti-PD1/L1 antibody as the treatment regimen immediately prior to accrual to this study or disease progression within 6 months of adjuvant anti-PD1 antibody.
- 4. Have measurable disease based on irRECIST 1.1.
- 5. Have a performance status of 0 or 1 on the ECOG Performance Scale.
- 6. Demonstrate adequate organ function as defined in Table 1.

Table 1 Adequate Organ Function Laboratory Values

System	Laboratory Value
Hematological	
Absolute neutrophil count (ANC)	≥1,500 /mcL
Platelets	≥100,000 / mcL
Hemoglobin	≥8 g/dL or ≥4.96 mmol/L
Renal	
Serum creatinine OR	≤1.5 X upper limit of normal (ULN) OR

Measured or calculated ^a creatinine clearance (GFR can also be used in place of creatinine or CrCl)	≥60 mL/min for subject with creatinine levels > 1.5 X institutional ULN
Hepatic	
Serum total bilirubin	≤ 1.5 X ULN OR
	Direct bilirubin ≤ ULN for subjects with total bilirubin levels > 1.5 ULN
AST (SGOT) and ALT (SGPT)	≤ 2.5 X ULN OR ≤ 5 X ULN for subjects with liver metastases
Albumin	≥2.5 mg/dL
^a Creatinine clearance should be calculated	per institutional standard.

- 7. Female subject of childbearing potential should have a negative urine or serum pregnancy within 72 hours prior to receiving the first dose of study medication. If the urine test is positive or cannot be confirmed as negative, a serum pregnancy test will be required.
- 8. Female subjects of childbearing potential should be willing to use 2 methods of birth control or be surgically sterile, or abstain from heterosexual activity for the course of the study through 120 days after the last dose of study medication (Reference Section 5.7.2). Subjects of childbearing potential are those who have not been surgically sterilized or have not been free from menses for > 1 year.
- 9. Male subjects should agree to use an adequate method of contraception starting with the first dose of study therapy through 120 days after the last dose of study therapy.

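### Does the pooled 70-patient response rate in section 10.1 need a named interval method and a separate rate for the last 35 patients?

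*Combined protocol and SAP*

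**What the plan says.** Section 10.1 specifies a Simon "optimal two-stage design will be employed to test the null hypothesis of a 10% response rate (based on historical ipilimumab alone) vs. a 30% alternative". The trial stops if at most 1 of 12 patients responds; otherwise it goes on to 35, and "if 6 or more (>17%) are seen the null hypothesis will be rejected and the treatment considered worthy of further testing". The stated properties are a one-sided alpha of 0.10, 90% power and a 0.65 probability of stopping early at a true 10%.

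The expansion, which the section ties to the closure of a cohort 2, follows: "we will enroll an additional 35 patients who had initial progression if 6 or more patients respond among the initial 35". Its purpose is to "provide additional precision for the estimated response rate and other secondary endpoints". The planning figure is that "assuming a true rate of 30%, n=70 subjects will provide a 90% confidence interval width" of ±9.0%. The section does not say how the interval is computed or whether the first and last 35 will be shown apart.

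On the population, section 4.2.3 speaks of "patients who have had initial progressive disease, or only disease stabilization, to anti-PD1/L1 antibody alone". Inclusion criterion 3 in section 5.1.2 requires progression on anti-PD1/L1 treatment or "disease progression within 6 months of adjuvant anti-PD1 antibody".

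**The concern.** Patients 1 to 12 are seen through a gate of 2 responses, and patients 1 to 35 through a gate of 6. Only the last 35 enter a 70-patient result unselected. Among trials that expand, the first 35 therefore look better on average than the truth, and pooling carries half of that excess into the final rate. The comparison is with a fixed historical 10%, so an inflated estimate could be read as activity.

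A result of 12/70 (17.1%, exact 90% interval 10.2–26.3%) illustrates the worry. It could arise as 8/35 then 4/35, with the last block at 11.4% (4.0–24.3%), or as 6/35 then 6/35, with the last block at 17.1% (7.7–31.1%). The plan would report both alike. The reference to a closed cohort 2, and the different wording in sections 4.2.3 and 5.1.2, also raise the question whether both blocks come from one population.

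**Working it through.** **Inputs, all from section 10.1:** stages of 12 and 23 patients, gates of at least 2/12 and at least 6/35, then 35 more; null 10%, alternative 30%; 90% interval at n = 70.

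**1. The plan's own figures.** Let X1 ~ Bin(12, p), X2 ~ Bin(23, p), X3 ~ Bin(35, p). Exact enumeration gives:
- alpha = P(X1 ≥ 2 and X1 + X2 ≥ 6 at p = 0.10) = 0.0977
- power = the same probability at p = 0.30 = 0.9014
- early stopping = P(X1 ≤ 1 at p = 0.10) = 0.659 (stated as 0.65)
- half-width at n = 70: 1.645 × √(0.3 × 0.7 / 70) = 0.0901, the stated ±9.0 points, so the planning figure is a Wald half-width.

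**2. Pooled rate given expansion.** The last 35 average p, so the pooled mean is (mean rate in the first 35 given both gates + p) / 2. At 10%: (19.2 + 10.0) / 2 = 14.6%. At 30%: (31.0 + 30.0) / 2 = 30.5%.

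| True rate | P(expand) | Mean pooled rate | Bias (points) | 90% coverage given expansion, exact / Wald |
|---|---|---|---|---|
| 10% | 9.8% | 14.6% | +4.6 | 75% / 87% |
| 15% | 33.7% | 18.0% | +3.0 | 93% / 93% |
| 20% | 60.4% | 21.8% | +1.8 | 95% / 94% |
| 30% | 90.1% | 30.5% | +0.5 | 92% / 90% |

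The bias is largest where expansion is rare. Counted over all trials, the probability of reaching n = 70 with an exact interval wholly above the truth is 2.4%, 2.4%, 2.9% and 4.7% at true rates of 10, 15, 20 and 30%, always below the nominal 5%. The sign of the bias also depends on the conditioning: averaged over all three stopping points, the final observed rate runs low (mean 7.3% at a true 10%, 28.3% at 30%).

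**3. Does the interval method matter?** For 21/70 the 90% limits are 21.0–39.0% (Wald), 21.1–40.3% (Clopper-Pearson) and 21.9–39.6% (Wilson). At a true 10%, prescribing the exact method would give lower conditional coverage than Wald (75% against 87%).

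**4. Does the split of 12/70 carry information?** With one p throughout, any path to 12/70 has probability proportional to p¹²(1 − p)⁵⁸. The weight for s responses in the first 35 is [Σ over x ≥ 2 of C(12, x) C(23, s − x)] × C(35, 12 − s), and p cancels when the weights are normalised. For s = 6, 7, 8 and 9 the probabilities are 0.355, 0.334, 0.206 and 0.082 at every p. Both 8 + 4 and 6 + 6 are ordinary outcomes, and which one occurs says nothing more about the response rate. An estimate adjusted for the gates could be computed from the total of 12/70 alone.

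**5. Is the last-35 rate the better estimate?** Its root mean squared error is √(p(1 − p)/35): 5.1, 6.0, 6.8 and 7.7 points at 10, 15, 20 and 30%. The pooled rate given expansion has 5.4, 4.7, 4.6 and 5.3. The last block wins only near 10%, and its half-width at 30% is 1.645 × √(0.21/35) = 12.7 points against 9.0.

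**6. One population?** Section 4.2.3 is rationale. Section 5.1.2 sets eligibility for every patient under the current text, before and after expansion. The remark about cohort 2 explains why more patients with initial progression can be enrolled; it does not say that their characteristics change.

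**The case for a change.** The strongest reply is that a reader of a 70-patient report sees only trials that expanded, so the conditional figures are the relevant ones. Moderate true rates are not remote: at 15% a third of trials expand with +3.0 points of bias, and at 20% three in five with +1.8. Section 10.1 names methods for progression-free survival and biomarkers but none for the primary rate. In an open-label, investigator-assessed trial, both the method and any split by block would then be chosen after the data are known.

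The conditional bias is real, and so is the missing method name. Neither makes the plan unsound. At 15% and 20% the ordinary intervals still cover 93–95% given expansion, so the stated uncertainty more than absorbs the bias. Reporting the last block beside an unadjusted pooled rate would leave the pooled bias where it is. It would also invite misreading, since the gates alone produce an expected drop from the first to the second block of 9.2, 6.0, 3.6 and 1.0 points at 10, 15, 20 and 30%. Showing the blocks would help to detect a change in case mix, but no passage indicates one.

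**Conclusion.** The concern does not hold. Followed as written, section 10.1 gives a valid test at 35 patients and, at the rate it plans for, a pooled estimate biased by only half a point with close to nominal coverage. The one sizeable distortion, +4.6 points and 75% exact coverage, needs a true rate of 10%, where 90.2% of trials never reach 70 patients. The unnamed interval method is missing detail, worth about one point at the upper limit for 21/70. A separate rate for the last 35 is a matter of preference: under a constant response rate it adds no information on that rate, and it is the less accurate estimate at 15, 20 and 30%. These conclusions rest on exact binomial calculation with the same response rate in both blocks. Evidence of a change in population between them would reopen the question, but the documents contain none.
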